### ***Exclusion Criteria***

- Staff at the four sites who are unable to converse in English or Spanish or are under 18 years of age.
- Parents  $< 18$  years of age, parents with children with SCA who are 13 years of age or older, parents whose child does not take daily penicillin or hydroxyurea, foster parents, caregivers who speak neither English nor Spanish, and caregivers previously enrolled in the study.

## *Patient Selection*

***Study 1 (Aim 1): The implementation of a practice-based social determinants of health screening and referral intervention in two pediatric hematology clinics to field test key study logistics and understand the facilitators and barriers to implementation and accelerate its adoption***

The site PI at each institution will help us identify staff members. The BMC-based team will provide an information sheet about Aim 1 of the study in advance so that practitioners and staff have time to consider the consent and come to the focus groups ready with questions regarding the consent. Before beginning the focus groups, the study PIs ([name]) and members of the research team will meet with clinic stakeholders at their staff meetings and provide an overview of the study. All eligible participants will be told that taking part in the research is voluntary and that the decision to not take part will not result in any loss of benefits to which they are entitled to or effect their employment. We

will schedule the focus groups at convenient times for the staff such as prior to beginning of a clinic session or during staff meetings. The Boston Medical Center-based team will conduct focus groups with pediatric hematology clinic staff every six months throughout the study period. We expect that there will be staff turnover during the study and we will be in regular communication with the medical director to monitor and make sure the research team is aware of this.

***Study 2 (Aim 2): Obtaining population-specific empirical estimates of study parameters to plan a future large-scale cluster RCT of WE CARE for children with SCA***

Eligible study participants will be identified by the research staff by reviewing the clinic schedule in advance. We will also ask front desk personnel to assist us in identifying potential subjects, if they are willing, and, in some sites, to assist in handing out informational flyers. If a family is identified as likely to meet eligibility criteria, a member of the study team will approach potentially eligible parents in a private location at the practice, such as an exam room. If the parent is eligible for the study, a study team member will review the study with him/her..

***Study 3 (Aim 3): Qualitatively assess possible mechanisms linking SDoH interventions to improved health outcomes, such as increasing a parent's ability to manage their child's disease through medication adherence***

Families will be enrolled from the two control sites (i.e., those in which the WE CARE intervention is not implemented). A research assistant at the two control sites will coordinate recruitment efforts, which will include telling potentially-eligible families about the study and conducting initial eligibility screening. Families who are both eligible and interested in participating will be scheduled for an interview, which will occur in the hematology clinic on the same day as a future routine medical visit to decrease participant burden. Study participants will be engaged in the interview only once; therefore, we will not need to retain participants in this study.

***Description of Study Treatments or Exposures/Predictors***

**WE CARE SDoH Screening and Referral intervention:** WE CARE is a relatively simple intervention that has two key components: (1) the WE CARE SDoH Screening Survey and (2) SDoH Community Resource sheets. The intervention will be fully implemented at two of four study sites, after which subjects will be enrolled to collect the outcomes described on pages 7-8, *Definition of Primary and Secondary Outcomes/Endpoints*.

**Table 1. Summary of the WE CARE Components.**

Key Components:	Description
WE CARE SDoH Screening Survey (see attachments)	Administered at all visits Identifies 6 unmet material needs and parent desire for assistance with: childcare, employment, food security, utilities (heating/cooling, water, electricity), housing, inadequate education 3 rd grade reading level; 0.92 test-retest reliability of original survey 
SDoH Community Resources	One-page information sheets listing available resources 5 th grade reading level

***Component 1: WE CARE SDoH Screening Survey.*** The survey consists of 12 questions designed to: (1) briefly identify 6 unmet material needs (e.g., childcare, employment, food security, household heat,

housing inadequate education) by self-report (e.g., “Are you employed?”) and (2) using a family-centered approach, determine whether parents would like assistance with each problem (i.e. “If no, do you want help?”). Parents wanting help will receive a resource referral (see below). The survey has been translated into Spanish. Because it is a component of the practice-wide implementation of the WE CARE SDoH screening and referral program, the survey will be given at all visits by the front desk staff to all parents of SCA patients who present to the pediatric hematology clinic—not solely to caregivers who enroll in the study. The front desk staff and/or research staff will instruct parents to complete the screener. Clinic staff will be trained to review the WE CARE SDoH survey at visits and to provide community resource information sheets to parents with needs (see below). The completed surveys will be scanned into the EHR.

*Component 2: Family Resource Book.* The Family Resource book will contain one-page information sheets listing community resources (e.g., food pantries) and their contact information (e.g., telephone number) for each specific material need (e.g., food insecurity). Information sheets will be specific to each site and written at, or below, the 8th grade level. The book will contain six separate tabs, one for each unmet need, and will contain multiple copies of the information sheets. The Family Resource Book will be made available in each exam room. We will work with each practice to create a Family Resource Book prior to study initiation. For parents with an identified need, providers will be instructed to give an information sheet and document this in the electronic health record (EHR), as done in previous studies.

### ***Definition of Primary and Secondary Outcomes/Endpoints***

Because qualitative research is by nature exploratory, we have not defined outcomes for the focus group discussions with practice staff (**Aim 1**); however, we will use the Promoting Action on Research Implementation in Health Services (PARIHS) framework to guide these discussions about facilitators and barriers to WE CARE implementation. Key areas of exploration will be (1) evidence: attitudes and beliefs about evidence of the WE CARE system; (2) context: organizational, systemic, and sociopolitical features that promote or hinder implementation of WE CARE; and (3) facilitation: attributes of the facilitation that supported or impeded the implementation, and needed adaptations.

Primary outcomes for **Aim 2** include the following:

- *Identification of unmet needs and provision of referrals.* Previously utilized forms will be used during baseline and follow-up questionnaires to measure whether practitioners provided families resource handouts.
- *Parental enrollment in community-based resources.* Baseline and follow-up questionnaires to measure enrollment in community resources.
- *Process measures.* Data will be collected on adherence to clinic visits (appointments kept, cancelled, and no-show). We will collect data on medications adherence in two ways. First, we will collect laboratory markers that are commonly affected by HU, including hemoglobin and hemoglobin F levels, white blood cell and absolute neutrophil counts, and MCV. We will also collect data on prescriptions written and filled for HU and penicillin through EHR review and parent report.
- *Health outcomes:* Data on vaso-occlusive episodes, acute chest syndrome and sepsis will be collected from the EHR at 6-month- and 12-month follow-up. Quality of life will also be assessed through both the PedsQL, which has been validated in children with sickle cell disease and is responsive to change, and the PedsQL Sickle Cell Disease Module.
- *Healthcare utilization outcomes:* Data on emergency department visits, hospitalizations, and clinic visits will be collected from the EHR at baseline and 12-month follow-up. We have chosen

emergency department visits as our primary outcome because it has been extensively, and commonly, used as a measure of lack of outpatient care and non-adherence to treatment regimens in this population. We will also calculate ED reliance (clinic visits kept / clinic visits kept + ED visits), as it has been used to discriminate frequent emergency department users.

Because qualitative research is by nature exploratory, we have not defined outcomes for the qualitative interviews with parents of children with SCA (**Aim 3**). Qualitative interviews will aim to examine parents' perceptions of factors that promote or hinder effective management of their child's SCA.

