Quality improvement methodology will be used to both gather key information and optimize the implementation of WE CARE. We will employ the Model for Improvement's Plan-Do-Study-Act (PDSA) methodology to assess the implementation of WE CARE in an iterative fashion for one year in each clinic. Best practices regarding key elements of the intervention will be continually assessed throughout the QI phase. [name] will initially meet weekly with clinic stakeholders via video conferencing to review the WE CARE process data and identify areas for improvement. We expect, based on our prior experience that we will gradually scale back to monthly meetings. This phase of the study will not involve human subjects.

*Intervention Fidelity Data:* Study staff, as we have previously done, will collect data on the implementation of WE CARE from the electronic health record (EHR). Specifically, to determine whether WE CARE *screeners were given and whether referrals were made at clinic visits*, and to assess for drift during the study period, we will measure the scanned surveys in the EHR for SCA visits. Of note, the WE CARE survey has a referral checkbox that providers mark if a referral is made. Clinical staff will be instructed to check off the box if she/he provides an information sheet from the Family Resource Book

for an unmet need. Every six months, we will randomly select 10 patients who had a visit and review their EHR for distribution of surveys and referrals. This study phase will not involve human subjects.

**Materials.** The research data will include audio-recordings of focus groups. Only study PIs [name], [name] (co-I), and trained study staff at each of the study sites will have access to participants' identifying information. The site PIs and RAs from the two control sites will not have access to the identifiable qualitative data. We will use excel spread sheets to document our descriptive QI and fidelity data (e.g., distribution of WE CARE surveys, unmet needs, referrals); no HIPAA identifiers will be collected.

***Study 2 (Aim 2): Obtaining population-specific empirical estimates of study parameters to plan a future large-scale cluster RCT of WE CARE for children with SCA***

**Study Procedures.** Parents will be asked to complete a baseline and 12-month follow-up questionnaire at their child's medical visit and complete a brief telephone interview 3, 6, and 9 months post-enrollment.

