## Statistical Power and Sample Considerations

We will enroll up to 235 subjects in this study, including up to 60 practice staff and 175 parents of children with SCA.

Because the goal for **Aim 1** is to examine the implementation of WE CARE in the outpatient pediatric hematology clinical setting our sampling will be purposeful. Based on our previous experience, we anticipate up to 15 practice staff per site will participate in focus group discussions.

For **Aim 2**, we are proposing to enroll 35 families from each of the four study sites (2 experimental, 2 control) to field test study logistics, including collecting empiric estimates of study parameters for a larger pragmatic trial. To demonstrate the feasibility of our study design, we use ED visits (primary

outcome) and penicillin adherence as examples. Assuming a 5% error rate, and based on our R00 WE CARE study, we expect a cluster coefficient no larger than 0.01. Based on recent data, we expect at least 80% of children in our control group to have at least one ED visit within our study observation period. We expect that our intervention group will have a much lower proportion, with ≤40% having with one or more ED visits. Our proposed study sample has >90% power to detect differences of at least 25% in the proportion of children with ED visits. In addition, based on estimates from the literature we expect a 9-month medication adherence of 40% and 10% in the intervention and control groups, respectively. Our study will have 90% power to detect differences of at least 20% in penicillin adherence, which is considered clinically significant. Consistent with CONSORT guidelines for pilot studies, we will not use results from this study to determine efficacy, since effects sizes from pilot studies likely overestimate or underestimate the true effect size; rather we will determine empiric estimates from the control group as the basis for power calculations for a future multi-site trial.

For **Aim 3**, in order to explore an array of beliefs and practices regarding family contextual factors that promote or prevent effective SCA management, enrollment will continue until saturation is reached (i.e. more interviews will not generate additional information) in primary research questions. Based on our previous experience, we expect 25-35 parents will be sufficient to reach saturation.

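### The Aim 2 referral outcome is described only as receipt of a resource handout, so referrals made by other routes, most likely at control clinics, would be missed

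*Combined protocol and SAP*

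**What the plan says.** Definition of Primary and Secondary Outcomes/Endpoints lists "Identification of unmet needs and provision of referrals" first among the Aim 2 primary outcomes. Its measurement is given in one sentence: forms from earlier work are to be used, at baseline and follow-up, to "measure whether practitioners provided families resource handouts". These are parent questionnaires; Data Collection Methods (Study 2) states that "Parents will be asked to complete a baseline and 12-month follow-up questionnaire at their child's medical visit".

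Description of Study Treatments names two key components of the intervention: "1) the WE CARE SDoH Screening Survey and (2) SDoH Community Resource sheets". Under Component 2 (Family Resource Book), providers are instructed to hand a sheet to any parent with an identified need. The same section puts the intervention at two of the four sites and starts family enrolment only after it is fully in place.

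One other referral record is described, under Intervention Fidelity Data: "the WE CARE survey has a referral checkbox that providers mark if a referral is made". Staff are told to tick it when they supply a sheet from the Family Resource Book.

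**The concern.** The outcome's label is broad and its described measure is narrow. The label covers finding needs and making referrals; the measure covers one mode of referral, which is also the act that WE CARE trains providers to perform. A control clinic that finds a need and refers the family through a social worker or a phone call has made a referral, yet a question about handouts would not record it.

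The contrast between arms would then partly reflect delivery of the intervention's own materials rather than referral behaviour, and the control referral rate would come out too low. Both matter in a pilot meant to supply planning estimates. The Data Analysis Plan compares the groups on its outcomes, and Statistical Power and Sample Considerations says of the pilot's use that "we will determine empiric estimates from the control group as the basis for power calculations for a future multi-site trial".

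**Working it through.** The plan gives no rate, effect size or power for the referral outcome, so there is no figure to reproduce. The check has two parts.

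**1. What each described source would record for a control family referred without a handout**

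- Parent questionnaire, as described: no handout, so no referral.
- Referral checkbox: it sits on the WE CARE survey, which is used only where WE CARE runs.
- Chart review (Data Collection Methods and Data Management Methods): the listed items are appointment attendance, prescription refills, hydroxyurea laboratory tests, ED visits, hospitalizations and clinical events. No social-needs screen, social-work contact or referral is listed.
- Telephone interviews at 3, 6 and 9 months: these ask about needs and about contact and enrolment with community services. They could show that the family reached a service, but they are not described as asking whether the clinic referred it.

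So the referral itself is missed, although its consequence may be seen. Baseline does not settle the matter: enrolment follows full implementation, so the baseline questionnaire at WE CARE sites may already reflect handouts.

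**2. Illustration of size (every rate is an assumption; none is in the documents)**

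Let H be the share of WE CARE families given a handout, c the share of control families given one, and b the share referred by another route, equal in both arms and independent of handouts.

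- Handout-only reading: H − c
- Any-route rate, WE CARE: 1 − (1 − H)(1 − b)
- Any-route rate, control: 1 − (1 − c)(1 − b)
- Any-route difference: (1 − b)(H − c)

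With H = 60% and c = 0, the case that gives the largest reading:

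| b | WE CARE, any route | Control, any route | Any-route difference | Handout-only reading | Overstatement |
|---|---|---|---|---|---|
| 10% | 1 − 0.4 × 0.9 = 64% | 10% | 54 | 60 | 6 |
| 30% | 1 − 0.4 × 0.7 = 72% | 30% | 42 | 60 | 18 |
| 50% | 1 − 0.4 × 0.5 = 80% | 50% | 30 | 60 | 30 |

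The control rate would be recorded as 0% in each row. If control clinics give handouts of their own (c > 0), the reading falls below 60. Under independence the ratio of reading to any-route difference stays at 1/(1 − b), that is 1.11, 1.43 and 2.00.

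The result depends on independence. If every WE CARE family referred by another route also received a handout, the WE CARE any-route rate stays at 60% and the differences are 60 − 10 = 50, 60 − 30 = 30 and 60 − 50 = 10. If the two routes never overlapped, they are 70 − 10 = 60, 90 − 30 = 60 and, with the rate capped at 100%, 100 − 50 = 50.

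**The case against.** The best defence is that one summary sentence is being read closely. The forms are described as previously used and are not in the documents; they may ask more than the sentence says. The fidelity section treats giving a sheet as the referral to be ticked, so handout receipt fits the study's own usage and is a legitimate proximal process measure. ED visits are named as the primary outcome, and the plan disclaims any efficacy conclusion. All of this stands. It limits the weight of the point, but does not show that a non-handout referral would be counted.

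Four stronger readings are tempting, and the documents do not support them.

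- *Every control referral scores as none.* The term resource handouts is generic, so a control clinic's own printed list could count. The plan also speaks of preparing a Family Resource Book with each practice, without expressly limiting this to the two intervention sites. A zero control reading is the extreme case.
- *The illustrated differences are 50, 30 and 10 points.* Subtracting an any-route control rate from a handout-only WE CARE rate uses two definitions of referral. It is correct only under the complete overlap shown above.
- *Active care at control clinics would go unseen, so a null ED result could not be interpreted.* Study Design plans staff focus groups at all four sites, the telephone interviews cover resource contact and enrolment, and control-site parents are interviewed in depth under Aim 3. None of these counts referrals, but all bear on how active the comparator was. The Background's remarks on screening recommendations and Medicaid incentives are general and describe none of the four clinics.
- *The future trial's power calculation will rest on an understated referral rate.* The power section promises control-group estimates in general. Its worked examples are ED visits and penicillin adherence, and it never names a referral rate.

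**Conclusion.** The point holds in limited form. As described, the referral outcome counts only handouts, and no other described source records a non-handout referral by a control clinic. The contrast on this one outcome may be inflated and the control referral rate understated. The amount cannot be established from the documents. Under the stated assumptions (60% handouts, no control handouts, equal and independent background referral), the overstatement is 6, 18 or 30 points for background rates of 10%, 30% or 50%. It disappears if no referrals are made by other routes, or if every such referral also comes with a handout.

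ED visits and the separate measures of resource contact and enrolment are untouched. This is a cheap improvement, not a defect that undermines Aim 2.

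**What to change.** **Outcome definition.** In Definition of Primary and Secondary Outcomes/Endpoints, keep the existing handout item but report it as a measure of fidelity. Define the referral outcome by a route-neutral item, asked for each need in identical form in both arms at baseline and follow-up:

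- Did the clinic ask about this need?
- Did anyone at the clinic give help or a referral for it by any route (handout, social worker, call, conversation, message)?

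If the existing forms already ask this, it is enough to say so in the outcome definition.

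**Chart review.** In Data Collection Methods (Study 2), add two yes/no fields for all enrolled children (planned 4 × 35 = 140): social-needs screen documented; social-work contact or community referral documented. These are independent of parent recall and of the WE CARE survey, and they give a record of usual care at the control clinics.

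**Cost.** A slightly longer questionnaire, two more fields in an abstraction already planned, and probably a smaller difference between arms on this outcome.

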***Aim 2. Obtain population-specific empirical estimates of study parameters to plan a pragmatic large-scale cluster RCT.*** We will summarize the number of parents contacted, lost to follow-up, refusing participation, and enrolled. We will examine this by gender (e.g., father vs. mother). We will note reasons for refusals. We will determine parents' recruitment and attrition rates and receipt of WE CARE using descriptive statistics. We will also determine the data collection completion rate, including hair cortisol, for each data time point (baseline, 3-, 6-, 9-, and 12-month follow-up) via descriptive statistics. Each outcome and process variable described above will be first transformed into its final composite value/score. We will calculate within-group mean and standard deviation of our SDoH, process, mediator and health utilization and health outcome variables. We will also break down the intervention group into two subgroups differentiated by whether parents enrolled in resources at follow-up, and explore any differences. An intention-to-treat approach will be used to explore differences between the intervention and control groups. We will also report all data disaggregated by gender. Two independent sample t-test and chi-square tests will be used to determine bivariate differences. Mixed effects regression models will be used to estimate the effect size of the intervention on SCA outcomes accounting for baseline differences in sociodemographics, types of SDoH, cumulative needs, receipt of services, and *a priori* determined covariates (i.e. sociodemographic characteristics). To explore potential moderators for the intervention effect at the parent, child and family levels (e.g., gender, race, ethnicity, age, language, household income), we will use Rothman's methodology; specifically, we will conduct stratified analyses for each potential moderator followed by using standard interaction terms in our models. We will also explore mediation of our hypothesized potential mediators between SDoH and the intervention with each SCA health outcome using the approach recommended by MacKinnon, Lockwood, and Williams. We will account for the clustering by study site by calculating the intraclass correlation.

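### ED reliance is defined by a formula that gives the clinic-visit share, so the score falls as emergency department use rises

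*Combined protocol and SAP*

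**What the plan says.** The section Definition of Primary and Secondary Outcomes/Endpoints lists healthcare utilization among the Aim 2 outcomes and singles out ED visits as the primary one. It then adds a derived measure: "We will also calculate ED reliance (clinic visits kept / clinic visits kept + ED visits" (the closing bracket follows). The reason given is "as it has been used to discriminate frequent emergency department users".

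The component counts come from the chart: "Data on emergency department visits, hospitalizations, and clinic visits will be collected from the EHR at baseline and 12-month follow-up".

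The Data Analysis Plan for Aim 2 has only a general scoring rule, "Each outcome and process variable described above will be first transformed into its final composite value/score", followed by the summary "We will calculate within-group mean and standard deviation of our SDoH, process, mediator and health utilization and health outcome variables". It also provides for exploring differences between the intervention and control groups. It does not restate the ED reliance formula, say whether a high value is good or bad, or reverse the score. No other section defines the measure.

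**The concern.** A measure called ED reliance should rise as a child depends more on the ED. The printed ratio has clinic visits kept on top, so it falls as ED visits rise. The document contains no other definition, so an analyst who follows it will code what is printed.

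If that score is then reported under its name, the mean level in each arm is misread and any between-arm difference is reported in the wrong direction. An intervention that reduced ED visits would appear to increase ED reliance. The same misreading would carry into the regression, moderator and mediation results for this variable, and into any control-group mean taken forward to plan the larger trial.

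**Working it through.** **Inputs.** Let C be the number of clinic visits kept and E the number of ED visits for one child. The formula is the one in the outcomes section. The document gives no visit counts per child, so the values of C and E below are assumptions for illustration.

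**Step 1: how to read the formula.** The denominator has no brackets of its own. Taken strictly, C / C + E equals 1 + E whenever C is above zero. For C = 4 and E = 8 that gives 9. This is not a proportion and does not depend on the number of clinic visits, so it is not a plausible intent. The sensible reading is C / (C + E).

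**Step 2: relation to the ED share.** The ED share is E / (C + E). Since C / (C + E) + E / (C + E) = 1, the printed score equals 1 minus the ED share for every child with at least one visit.

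**Step 3: numbers.**

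| C | E | Printed score C/(C+E) | ED share E/(C+E) |
|---|---|---|---|
| 4 | 0 | 1.00 | 0.00 |
| 4 | 1 | 0.80 | 0.20 |
| 4 | 2 | 0.67 | 0.33 |
| 4 | 4 | 0.50 | 0.50 |
| 4 | 8 | 0.33 | 0.67 |
| 1 | 4 | 0.20 | 0.80 |
| 0 | 3 | 0.00 | 1.00 |
| 0 | 0 | undefined | undefined |

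With C fixed at 4, a fall in ED visits from 4 to 2 moves the printed score by 0.67 − 0.50 = +0.17 and the ED share by 0.33 − 0.50 = −0.17.

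**Step 4: what changes at group level.** Let m be an arm's mean ED share.

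- The mean printed score is 1 − m. A printed mean of 0.80 corresponds to an ED share of 0.20.
- The between-arm difference in the printed score is (1 − m₁) − (1 − m₀) = −(m₁ − m₀). It has the same size and the opposite sign.
- Subtracting every value from 1 leaves the standard deviation and the intraclass correlation unchanged. A t statistic keeps its absolute value, and so its two-sided p-value.

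These are identities and hold for any visit rates.

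**Step 5: what does not depend on the score.** The power statement reads "Our proposed study sample has >90% power to detect differences of at least 25% in the proportion of children with ED visits". It rests on whether a child has any ED visit, not on this ratio. The primary outcome, ED visits, is likewise separate.

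**The case against.** The strongest reply is that this is a wording slip on a supporting measure in a pilot. The protocol says it will not judge efficacy from these data. The quantities most useful for planning the next trial, the standard deviation and the intraclass correlation, are the same under either form. The control mean is recovered by subtracting from 1, and the raw counts are collected in any case. Harm needs two steps: coding the ratio as printed, and then reading it by its name without noticing that children with no ED visits score 1. All of this stands, and it limits the consequence.

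Two narrower points also have force. The purpose clause does not itself contradict the formula, because a score and its complement separate frequent ED users equally well: a low clinic share flags them just as a high ED share does. The conflict is between the name and the formula. Also, the reading depends on supplying brackets, and a reader who has to repair the brackets may query the numerator too.

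None of this removes the defect. Missing brackets do not explain why clinic visits are in the numerator, and nothing else in the document puts it right. The written definition is what will be programmed.

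**Conclusion.** The concern holds. As written, ED reliance is the clinic-visit share, and its name and formula run in opposite directions. If it is coded as printed and interpreted by name, each mean m is reported as 1 − m and each between-arm difference has the right size and the wrong sign.

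The conclusion rests on one assumption, that the denominator is meant to be the sum of both visit types. The visit counts used for illustration do not matter to it. The effect is confined to this derived measure. It should be corrected before the variable is programmed, but it does not threaten the main analysis.

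**What to change.** Make the name and the formula agree, write the brackets out and state the direction. There are two equivalent ways:

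- ED reliance = ED visits / (ED visits + clinic visits kept), with higher values meaning more reliance on the ED; or
- keep the ratio as clinic visits kept / (clinic visits kept + ED visits), rename it the clinic-visit share, and state that higher values mean less reliance on the ED.

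In the same sentence, say how a child with no visits of either kind in the period is handled, since the ratio is then undefined. Repeat the definition in the Data Analysis Plan, where the composite scores are formed.

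The cost is a one-line wording correction. It needs no new data and changes neither the sample size nor the primary outcome. If the score has already been computed as printed, subtracting it from 1 gives the ED share.
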